Abbreviations: AEs = adverse events; BMI = body mass index; BP = blood pressure, CBC = complete blood count; COVID-19 = coronavirus disease 2019; CRU = clinical research unit; DAR = drug-antibody ratio; ECG = electrocardiogram; FSH = follicle-stimulating hormone; HBV = hepatitis B virus; HCV = hepatitis C virus; HIV = human immunodeficiency virus; HR = heart rate; hr = hour; ICF = informed consent form; OV = outpatient visit; PK = pharmacokinetic; RR = respiration rate; SARS-CoV-2 = severe acute respiratory syndrome coronavirus 2.

Schedule of Events: First Single Dose, Cohorts 1A, 1B, 2A, 2B, 3A, and 3B

- For subjects in Cohorts 1A and 1B: outpatient visits will occur at Day 45 (OV1), Day 60 (OV2), Day 90 (OV3), and Day 120 (OV4). For subjects in Cohorts 2A, 2B, 3A, and 3B, timing of outpatient visits will occur at Day 45 (OV1), $\sim 2 \times t_{1/2}$ (OV2), $\sim 3 \times t_{1/2}$ (OV3), and $\sim 4 \times t_{1/2}$ (OV4), pending PK data from Cohorts 1A and 1B. If 2 half-lives have passed by OV2, the visit may be omitted.
- For subjects who discontinue study early, the OV4 procedures should be performed.
- For subjects in Cohorts 2A, 2B, 3A, and 3B, reconfirmation of inclusion and exclusion criteria (retesting of FSH not required) is to be completed at second single dose period's CRU check-in and prior to the second single dose of CD388 Injection or placebo.
- On Day 1, the targeted physical examination should be performed predose. Vital signs collection will occur predose, 6 hours postdose, and as clinically indicated.
- 12-lead ECG is to be performed at screening, at CRU check-in on Day -1, predose (immediately prior to study drug administration) and 6 hours postdose (± 10 minutes) on Day 1, and as indicated in the Schedule. Subjects are to be resting and semi-recumbent when ECG is being conducted.

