- k. At indicated visits, inspection of administration site and surrounding area will be performed twice daily (once between approximately 2–4 hours postdose, and once approximately 8–12 hours postdose), with any abnormal findings reported as AE s. Reactions will be rated according to the scale provided in [Table 7](#).
- l. For Cohorts 1A, 1B, 2A, 2B, 3B: Blood samples for PK analysis will be collected predose (-24 hour window); post-dose at 2, 4, and 12 hours (each \pm 10 minute window); 24 hours (\pm 30 minute window); 48 hours (\pm 1 hour window); 72, 96, 120 hours (each \pm 2 hour window); and Days 7, 9, 11, 14, 21, 30 (each \pm 2 hour window). Postdose samples collected at outpatient CRU visits at OV1, OV2, OV3, and OV4 have the same windows (i.e., in \pm days) as the visits.
For Cohort 3A: Blood samples for PK analysis will be collected predose (-24 hour window); post-dose at 12 and 24 hours (\pm 30 minute window); 48 hours (\pm 1 hour window); 72, 84, 96, 108, 120 hours (each \pm 2 hour window); and Days 7, 9, 11, 14, 21, 30 (each \pm 2 hour window). Postdose samples collected at outpatient CRU visits at OV1, OV2, OV3, and OV4 have the same windows as the visits.
- m. Blood samples for metabolite identification (e.g., free zanamivir, zanamivir dimers) and CD388 DAR distribution will be collected on Day 1 at 2 hours postdose, on Day 2 at 24 hours postdose, on Days 14 and 30, and at OV3. Urine samples for metabolite identification will be collected on Day 1 from 0–12 hours and from 12–24 hours postdose, on Day 2 from 24–48 hours postdose, on Day 14 over a 24-hour period, and over a 24-hour period that starts on Day 29 and ends prior to CRU check-out on Day 30.
- n. Serum samples for CD388 glycoforms will be collected predose on Day 1 and once in the morning on Days 2, 7, 14, 21, and 30, and at the OV1 and OV3 visits.
- o. A mandatory pharmacogenomic (DNA) blood sample will be collected once, preferably on Day 1 (collection at another time point is allowed if necessary) to allow for pharmacogenomic research related to CD388.
- p. Nasopharyngeal swab samples will be collected predose on Day 1, and on Days 2, 5, 7, 9, 11, 14, 21, and 30.
- q. Adverse events (including influenza-like illness which will be tested for both COVID-19 and flu) will be collected for all subjects from the time of signing the ICF through 4 months after the last dose of study drug, whichever is longer.

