Subjects in Cohorts 2A and 2B and Cohorts 3A and 3B will receive a second single dose of CD388 Injection or placebo after washout of 5 effective half-lives after the first dose if it is determined that the safety and tolerability of the first dose is acceptable upon review of the cumulative safety data. Immediately prior to the second single dose, within each dose and route, any dropouts in the sentinel groups will be randomly replaced with subjects from the main groups, retaining their original treatment assignment (i.e., subjects assigned to placebo will remain placebo, and subjects assigned to CD388 will remain CD388; this may require unblinded personnel to oversee).

The PI and Sponsor will review blinded safety data after the initial sentinel group subjects at a dose level have completed dosing and followed for the minimum observation period as determined during the first single dose. If no drug-related SAEs or drug-related Grade ≥ 3 AEs have occurred, the subjects in the corresponding main group may be dosed within 24 hours.

The dose escalation scheme is presented in [Section 1.2](#).

The Schedule of Events is presented in [Table 1](#) (first single dose, Cohorts 1A, 1B, 2A, 2B, 3A, 3B), [Table 2](#) (second single dose, Cohorts 2A, 2B, 3A, and 3B), and [Table 3](#) (single dose, Cohort 4B). All subjects will be admitted to the clinical research unit (CRU) for observation and safety assessments from Day -1 (check-in) to Day 30. Subjects will be monitored for AEs (including reactogenicity/injection site reactions and hypersensitivity reactions) and SAEs as indicated below:

Cohort	AE/SAE monitoring period from signing of ICF:
1A, 1B	Through 4 months after the dose of study drug
2A, 2B, 3A, 3B, 4B	Through 205 days after the last dose of study drug (Day 206 ±10 days)

Abbreviation: ICF = informed consent form.

Safety will also be assessed by physical examinations, ECGs, vital signs measurements, and laboratory evaluations (hematology, coagulation, serum chemistry, and urinalysis) at various time points during and after the CRU stay. Concomitant medication use will be recorded throughout the study.

Continuous 12-lead digital ECG recording will be performed using a 12-lead Holter ECG monitor as indicated below:

Cohort	Holter Monitoring Period
1A, 1B	1 hour before administration of study drug until 48 hours after dosing
2A, 2B, 3B	1 hour before first administration of study drug until 48 hours after dosing ^a

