6.5. Expected Duration of Subject Participation

A single dose of study drug will be administered IM or SQ on Day 1. Study participation will require up to 28 days for screening procedures, and ~120 days for the first single dose (check-in to the CRU on Day -1; CRU inpatient stay for study drug administration, observation, and assessments and procedures for 31 days [Days -1 to Day 30]; and 4 CRU outpatient visits for additional assessments and procedures).

Subjects in Cohorts 2A, 2B, 3A, and 3B who receive a second single dose will have an additional 168 days of participation, with similar study visits to that of the first administration.

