7.4. Subject Withdrawal Criteria

7.4.1. Subject Stopping Rules

Subjects in Cohorts 2A, 2B, 3A, and 3B will be followed through Outpatient Visit 4 (OV4) of the first dosing period, and will not receive the second single dose:

- If the subject develops anaphylaxis or a related Grade 3 or Grade 4 AE
- If the subject has a persistent (i.e., >5 days with no response to treatment) Grade ≥ 2 rash considered related to the investigational drug by the Principal Investigator ([Appendix 4](#))
- If the Investigator believes that it is in the best interest of the subject to not receive a second dose
- If the subject no longer meets all eligibility criteria prior to the second single dose
- If the subject becomes pregnant prior to the second single dose

If a subject is removed from the study for any reason, the subject will be followed for resolution of any ongoing AE(s).

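### For Cohorts 2A, 2B, 3A and 3B, the Table 1 footnote ends AE collection at 4 months while the AE and TEAE window runs to 205 days, so subjects who miss the second dose have part of that window with no scheduled collection

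*Protocol*

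**What the plan says.** Table 1 is headed "Schedule of Events: First Single Dose, Cohorts 1A, 1B, 2A, 2B, 3A, and 3B". Its footnote q applies to all subjects on the table and collects AEs "through 4 months after the last dose of study drug, whichever is longer". SAP Appendix A carries the same footnote.

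Protocol Section 6.1 sets the AE/SAE period by cohort. For 1A and 1B it is "Through 4 months after the dose of study drug". For 2A, 2B, 3A, 3B and 4B it is "Through 205 days after the last dose of study drug (Day 206 ±10 days"). Sections 9.10, 11.2 and 11.5.3 and the synopsis repeat this split, and Section 12.3 uses it to define a TEAE. Table 2 footnote m (second dose, Cohorts 2A–3B) and Table 3 footnote o (Cohort 4B) also give 205 days, and both make the final AE assessment a phone call.

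Under Section 7.4.1, a Cohort 2A–3B subject who meets a stopping rule "will be followed through Outpatient Visit 4 (OV4) of the first dosing period, and will not receive the second single dose". In that period OV4 falls at about 4 half-lives, "pending PK data from Cohorts 1A and 1B", with no calendar day fixed. Section 6.5 allows approximately "120 days for the first single dose".

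**The concern.** Table 1 gives a shorter AE collection period for Cohorts 2A–3B than the sections that define the AE/SAE and TEAE windows, and its closing phrase implies a second term that is absent.

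For a subject who receives both doses this has little effect, because Table 2 footnote m takes over and states 205 days. For a subject who receives only the first dose, that dose is the last dose and Table 1 is the only schedule that applies. It ends at OV4 and has no Day 206 contact.

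At stake is the primary endpoint, TEAE incidence and severity after a single dose. A new event late in the window would count as a TEAE under Section 12.3, yet no scheduled contact would find it. The reasons for withholding the second dose include anaphylaxis, a related Grade 3 or 4 AE and a persistent related rash, so the shortened collection falls on a group partly defined by safety events. Each of these cohorts has only 8 CD388 subjects.

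**Working it through.** **1. Reproduce the plan's own figure.** Day 1 is the dosing day, so 205 days after dosing is 1 + 205 = Day 206. With ±10 days the range is Day 196 to Day 216. This agrees with Section 6.1.

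**2. Where the conflict lies.**

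| Cohorts | Planned n | Schedule footnote | Sections 6.1 and 12.3 | Conflict |
|---|---|---|---|---|
| 1A, 1B | 2 × 11 = 22 | 4 months (Table 1, q) | 4 months | No |
| 2A, 2B, 3A, 3B | 4 × 11 = 44 (32 CD388, 12 placebo) | 4 months (Table 1, q); 205 days (Table 2, m) | 205 days | Yes |
| 4B | 11 | 205 days (Table 3, o) | 205 days | No |

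The conflict therefore concerns cohorts with 44 of the 77 planned subjects. In practice it bites only on those among the 44 who are not given the second dose. The documents do not give that number.

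**3. Gap if footnote q is followed.** Four calendar months last 120 to 123 days depending on the start date, so collection ends at about Day 121 to Day 124. The shortfall is 205 − 123 = 82 to 205 − 120 = 85 days.

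**4. Gap if AEs are collected to OV4.** Table 1 marks AE assessment at every outpatient visit, including OV4. The OV4 day is 4 × half-life and has to be assumed:

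- *OV4 near Day 120.* This follows the approximate first-period length in Section 6.5 and corresponds to a half-life of 30 days (4 × 30 = 120). Gap: 206 − 120 = 86 days.
- *OV4 near Day 168.* This borrows the Table 2 visit days, which would fit a half-life of 42 days (84/2 = 126/3 = 168/4 = 42). Gap: 206 − 168 = 38 days. With OV4 ±14 and Day 206 ±10, the range is 196 − 182 = 14 to 216 − 154 = 62 days.
- *No gap.* OV4 reaches 205 days only if the half-life is about 205/4 = 51 days.

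The gaps in steps 3 and 4 are alternatives and do not add. If OV4 is near Day 168, Table 1 schedules an AE assessment after its own footnote's cut-off.

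**5. Does anything else close the gap?**

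- Section 11.6 follows unresolved SAEs and drug-related AEs; it does not look for new ones.
- Section 11.3.1 asks for SAEs after the study period only if the investigator learns of them and believes them causally related.
- SAP Section 8.1 defines a TEAE with no end date, so it does not settle the matter.

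**The case against.** The strongest reply is that this is one stale footnote and its copy. The synopsis and five numbered sections all state 205 days after the last dose for Cohorts 2A–3B, and a subject with one dose has a last dose, so those sections already cover that subject. A site that follows them would not stop at 4 months. This stands as far as the intended rule goes, and it means the 82–85 day gap arises only if the footnote is followed. It does not supply a contact: the phone call is attached only to Tables 2 and 3.

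The second reply concerns Section 7.4.1. A reader might infer that its OV4 rule is a third AE window that conflicts with the other two. It is not. It is a visit rule and states no AE end date, and Table 2 shows that a Day 168 OV4 and a Day 206 AE call can stand together. There are two conflicting AE windows and a last-visit rule with no later AE contact.

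Third, the provisions in Sections 11.6 and 11.3.1 do catch some events. What remains exposed is mainly new AEs that are non-serious or not considered related, in a group that may be small or empty.

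**Conclusion.** The contradiction is real for Cohorts 2A, 2B, 3A and 3B. For subjects in these cohorts who miss the second dose, part of the Section 12.3 TEAE window has no scheduled AE collection: about 82–85 days if footnote q is followed, or, if collection runs to OV4, about 86 days with OV4 near Day 120 and about 38 days with OV4 near Day 168. The OV4 days are assumptions, and those gaps are stated before visit windows.

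Three stronger readings are not supported. A reader might infer that footnote q conflicts with the rest of the protocol for every cohort; 1A and 1B have 4 months throughout, and 4B is not on Table 1. A reader might take all 44 subjects as affected; that is the planned cohort total. And a reader might suppose that second doses are mostly withheld for AEs; Section 7.4.1 also lists pregnancy, loss of eligibility and investigator judgment, and no frequencies are given.

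The point merits correction because a stated collection rule contradicts the window used to analyse the primary endpoint. It is a modest point, since the other sections agree with each other.

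**What to change.** Reconcile footnote q in Protocol Table 1, and its copy in SAP Appendix A, with the cohort table in Section 6.1, and remove the comparison that has no second term. Add to Table 1 a final AE phone contact for Cohort 2A–3B subjects not given the second dose, using the mechanism already in Tables 2 and 3, so that AE collection ends on the same date as the Section 12.3 TEAE window. The stopping rule in Section 7.4.1 need not change.

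The cost is edits to one footnote in two documents, one added contact in the schedule, and one call per affected subject.

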1.1.2. Second Single Dose, Cohorts 2A, 2B, 3A, and 3B

Table 2: Schedule of Events: Second Single Dose, Cohorts 2A, 2B, 3A, and 3B

Day (Window)	Clinical Research Unit (CRU) Inpatient Stay										Outpatient CRU Visits ^a			
	-1 (±10)	1	2	3-6	7	9	11	14	21	30	OV1 (±3)	OV2 (±5)	OV3 (±7)	OV4 ^b (±14)
Inclusion/Exclusion criteria ^c	X	X												
Complete physical with vital signs (BP, RR, HR, oral temperature, height, weight, BMI)	X													
Targeted physical with vital signs (BP, RR, HR, oral temperature)		X ^d	X	X	X			X	X	X	X	X	X	X
Safety ECG ^e	X	X			X					X				X
Laboratory evaluations (CBC with/platelets, serum chemistry, urinalysis)	X		X	X ^f	X			X	X	X	X	X	X	X
Virology screening (HBV, HCV, HIV)	X													
Virology screening (SARS-CoV-2)	X													
Urine Pregnancy ^g	X													
Drug/alcohol screen ^h	X													
Dosing of Study Drug (Cohorts 2 and 3 only)		X												
Reactogenicity/injection site inspection ⁱ		X	X	X										
PK sample collection ^j		X	X	X	X	X	X	X	X	X	X	X	X	X
Samples for metabolite identification ^k		X	X					X		X				X
Exploratory biomarker samples		predose		X ^f										
Anti-drug antibodies		predose						X		X	X	X	X	X
Nasopharyngeal swab/nasal wash collection ^l		predose	X	X	X	X	X	X	X	X				
Assess and record AEs ^m	X	X	X	X	X	X	X	X	X	X	X	X	X	X
Concomitant medications/procedures review ⁿ	X	X	X	X	X	X	X	X	X	X	X	X	X	X

Abbreviations: AEs = adverse events; BMI = body mass index; BP = blood pressure, CBC = complete blood count; COVID-19 = coronavirus disease 2019; CRU = clinical research unit; ECG = electrocardiogram; HBV = hepatitis B virus; HCV = hepatitis C virus; HIV = human immunodeficiency virus; HR = heart rate; hr = hour; ICF = informed consent form; PK = pharmacokinetic; RR = respiration rate; SARS-CoV-2 = severe acute respiratory syndrome coronavirus 2.

Schedule of Events: Second Single Dose, Cohorts 2A, 2B, 3A, and 3B

- a. For subjects in Cohorts 2A, 2B, 3A, and 3B: outpatient visits will occur at Day 45 (OV1), Day 84 (OV2), Day 126 (OV3), and Day 168 (OV4).
- b. For subjects who discontinue study early, the Day 168 procedures should be performed.
- c. Reconfirmation of inclusion and exclusion criteria (retesting of FSH not required) is to be completed at CRU check-in on Day -1 and prior to the second single dose of CD388 Injection or placebo on Day 1.
- d. On Day 1, the targeted physical examination should be performed predose. Vital signs collection will occur predose, 6 hours postdose, and as clinically indicated.
- e. 12-lead ECG is to be performed at CRU check-in on Day -1, predose (immediately prior to study drug administration on Day 1) and 6 hours postdose (± 10 minutes), and as indicated in the Schedule. Subjects are to be resting and semi-recumbent when ECG is being conducted.
- f. Laboratory evaluations need to be performed once during the Day 3–6 interval.
- g. Urine pregnancy test is required for females of childbearing potential at CRU check-in on Day -1.
- h. Drug and alcohol screen is to be performed during the outpatient visits if vital signs are abnormal (see [Appendix 2](#)).
- i. At indicated visits, inspection of administration site and surrounding area will be performed twice daily (once between approximately 2–4 hours postdose, and once approximately 8–12 hours postdose), with any abnormal findings reported as AEs. Reactions will be rated according to the scale provided in [Table 7](#).
- j. Blood samples for PK analysis will be collected predose (-24 hour window); post-dose at 24 hours (± 30 minute window); 48 hours (± 1 hour window); 72, 96, 120, 144, 168 hours (each ± 2 hour window); and Days 9, 10, 11, 12, 14, 21, 30 (each ± 2 hour window). Postdose samples collected at outpatient CRU visits on Days 45, 60, 90, and 120 have the same windows (i.e., in \pm days) as the visits.
- k. Blood samples for metabolite identification (e.g., free zanamivir, zanamivir dimers) will be collected on Day 1 at 2 hours postdose, on Day 2 at 24 hours postdose, on Day 30, and on Day 90. Urine samples for metabolite identification will be collected on Day 1 from 0–48 hours, from 48–96 hours, and from 96–144 hours postdose, on Day 14 over a 24-hour period, and over a 24-hour period that starts on Day 29 and ends prior to CRU check-out on Day 30.
- l. Nasopharyngeal swab samples will be collected predose on Day 1, and on Days 2, 5, 7, 9, 11, 14, 21, and 30. Nasal wash collection will occur at the time of C_{max} as determined from the first single dose (approximately 144 hours after dosing).
- m. Adverse events (including influenza-like illness which will be tested for both COVID-19 and flu) will be collected for all subjects as indicated below:

Cohort	AE/SAE monitoring period from signing of Informed Consent Form:
1A, 1B	Through 4 months after the dose of study drug
2A, 2B, 3A, 3B	Through 205 days after the last dose of study drug (Day 206 ± 10 days)

Note: the final AE assessment will be conducted via a follow-up phone call to the subject.

- n. Concomitant procedures used to treat an AE will be recorded from the time of CD388 Injection/placebo administration until the final study visit.

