- For Cohorts 1A, 1B, 2A, 2B, 3B: Continuous 12-lead digital ECG recording will be performed using a 12-lead Holter ECG monitor. Pharmacodynamic ECG tracings, including all 12-leads and of 10 seconds duration, will be extracted in triplicate for 5-minute observation periods at 60, 45, and 30 minutes predose; and at 2, 4, 6, 8, 10, 12, 24, 30, 36, and 48 hours postdose (expected time to maximum concentration is 1 to 2 days after administration). The Holter monitor will be removed on Day 3. The Holter monitor may be removed once on Day 2 for up to 15 minutes for shower/bathing, at least 2 hours away from the next ECG timepoint (i.e., 30, 36, or 48 hours postdose).
For Cohort 3A: Continuous 12-lead digital ECG recording will be performed using a 12-lead Holter ECG monitor. Pharmacodynamic ECG tracings, including all 12 leads and of 10 seconds duration, will be extracted in triplicate at prespecified time points for a 5-minute observation period starting from 1 hour before dosing, then at 72, 76, 80, 84, 96, 102, 106, 110, 118, and 120 hours after administration of study drug, and stored in a digital format. The Holter monitor may be removed once on Day 5 for up to 15 minutes for shower/bathing, at least 1 hour away from the next ECG timepoint. The Holter monitor will be removed on Day 6.

Schedule of Events: First Single Dose, Cohorts 1A, 1B, 2A, 2B, 3A, and 3B (continued)

- g. Laboratory evaluations need to be performed once during the Day 3–6 interval.
- h. Performed at screening, and as clinically indicated (e.g., if the Investigator has concerns regarding an SAE, anti-drug antibody reaction in a subject with hypersensitivity reaction, fever, serious rash, joint/bone pain, cough, proteinuria, or clinically meaningful changes in the white cell differential or liver function tests).
- i. A sensitive serum pregnancy test (β -human chorionic gonadotropin) is required at screening and OV4 for females of childbearing potential. FSH (if applicable to confirm postmenopausal status) is only required once. Urine pregnancy test may be performed at all other time points.
- j. Drug and alcohol screen is to be performed during the outpatient visits if vital signs are abnormal (see [Appendix 2](#)).

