[figure not shown]
Schedule of Events: Single Dose, Cohort 4B

- For subjects who discontinue study early, the Day 206 procedures should be performed.
- On Day 1, the targeted physical examination should be performed predose. Vital signs collection will occur predose, 6 hours postdose, and as clinically indicated.
- 12-lead ECG is to be performed at screening, at CRU check-in on Day -1, predose (immediately prior to study drug administration) and 6 hours postdose (± 10 minutes) on Day 1, and as indicated in the Schedule. Subjects are to be resting and semi-recumbent when ECG is being conducted.
- Continuous 12-lead digital ECG recording will be performed using a 12-lead Holter ECG monitor. Pharmacodynamic ECG tracings, including all 12-leads and of 10 seconds duration, will be extracted in triplicate for 5-minute observation period starting from 1 hour before dosing, then at 72, 76, 80, 84, 96, 102, 106, 110, 118, and 120 hours after administration of study drug, and stored in a digital format. The Holter monitor will be removed on Day 6. The Holter monitor may be removed once on Day 5 for up to 15 minutes for shower/bathing, at least 1 hour away from the next ECG timepoint.
- Laboratory evaluations need to be performed once during the Day 3–6 interval.
- Performed at screening, and as clinically indicated (e.g., if the Investigator has concerns regarding an SAE, anti-drug antibody reaction in a subject with hypersensitivity reaction, fever, serious rash, joint/bone pain, cough, proteinuria, or clinically meaningful changes in the white cell differential or liver function tests).
- A sensitive serum pregnancy test (β -human chorionic gonadotropin) is required at screening and OV4 for females of childbearing potential. FSH (if applicable to confirm postmenopausal status) is only required once. Urine pregnancy test may be performed at all other time points.
- Drug and alcohol screen is to be performed during the outpatient visits if vital signs are abnormal (see [Appendix 2](#)).
- At indicated visits, inspection of administration site and surrounding area will be performed twice daily (once between approximately 2–4 hours postdose, and once approximately 8–12 hours postdose), with any abnormal findings reported as AEs. Reactions will be rated according to the scale provided in [Table 7](#).

Schedule of Events: Single Dose, Cohort 4B (continued)

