11.8. Risks for Women of Childbearing Potential or During Pregnancy

The risks of CD388 Injection in pregnant or lactating/nursing women are unknown. Pregnant or nursing female subjects are excluded from this study.

Subjects must be instructed to inform the Investigator immediately if they or their partner becomes pregnant during the study. In the case of a partner pregnancy, partner informed consent must be attained prior to collecting information related to the pregnancy and to allow the Investigator to follow them for the outcome of the pregnancy. In the event of a confirmed pregnancy, the following actions should be taken:

- The pregnancy should be reported to the Sponsor within 24 hours of the subject notifying the Investigator using the applicable Pregnancy Report Form.
- The Investigator should counsel female subjects regarding the possible effects of CD388 Injection exposure on the fetus and the need to inform the study site of the outcome of the pregnancy.
- The subject or subject's partner, if consented, should be monitored until the postnatal day 28 or until termination of the pregnancy. The outcome should be reported using the Pregnancy Outcome or Abnormal Pregnancy Outcome form.

Pregnancy is not an AE, in and of itself. However, any pregnancy complication or elective termination of a pregnancy for medical reasons will be recorded as an AE or SAE.

A spontaneous abortion is always considered an SAE and will be reported as described in the AE and SAE sections. Furthermore, any SAE occurring as an adverse pregnancy outcome post-study must be reported to the Medical Monitor.

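### No pregnancy test is scheduled after the second dose in Cohorts 2A, 2B, 3A and 3B, although both other schedules test after dosing

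*Protocol*

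**What the plan says.** **Second dose (Table 2, Section 1.1.2).** The pregnancy row has one mark, in the Day -1 column. Footnote g names the same single time point: "Urine pregnancy test is required for females of childbearing potential at CRU check-in on Day -1". Footnote a places the outpatient visits OV1–OV4 on Days 45, 84, 126 and 168, and none of them carries a test. Footnote b adds: "For subjects who discontinue study early, the Day 168 procedures should be performed". Footnote m makes the last contact (Day 206) a telephone call. SAP Appendix B reproduces the row and the footnotes.

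**First dose (Table 1, Section 1.1.1).** Tests are marked at the outpatient visits. A serum test "is required at screening and OV4 for females of childbearing potential", with a urine test allowed at the other marked visits. On early exit, "For subjects who discontinue study early, the OV4 procedures should be performed".

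**900 mg, Cohort 4B (Table 3, Section 1.1.3).** Tests are marked on Days 30, 45, 84, 126, 168 and 206. On early exit, "For subjects who discontinue study early, the Day 206 procedures should be performed".

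**Pregnancy risk.** Section 11.8 states: "The risks of CD388 Injection in pregnant or lactating/nursing women are unknown". Inclusion criterion 3a (Section 7.1) requires highly effective contraception until 205 days after the last dose. Section 11.8 also says: "The pregnancy should be reported to the Sponsor within 24 hours of the subject notifying the Investigator".

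**The concern.** Tables 1 and 3 show that the protocol's own standard is to test women of childbearing potential during follow-up as well as before dosing. Table 2 departs from that standard without giving a reason, and it does so for the only subjects who are dosed twice.

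What is at stake is the detection of exposure during pregnancy. The 24-hour report to the Sponsor is timed from the woman's own notification. Counselling and outcome follow-up under Section 11.8 likewise start only once a pregnancy is confirmed. An unrecognised pregnancy after a repeat dose would trigger none of these steps.

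**Working it through.** No power, sample-size or error-rate figure is involved. The check counts the marked cells in each pregnancy row and looks for any other text that could supply the missing tests.

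**Scheduled post-dose tests**

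| Schedule | Post-dose visits with a test | Count | Test at early exit |
|---|---|---|---|
| Table 1, first dose | OV1–OV4 (SAP Appendix A also marks Day 30) | 4 (5) | Yes (OV4 procedures) |
| Table 2, second dose | none | 0 | No (Day 168 procedures) |
| Table 3, 900 mg | Days 30, 45, 84, 126, 168, 206 | 6 | Yes (Day 206 procedures) |

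For Cohorts 2A to 3B, Table 1 footnote a allows OV2 to be omitted, so that count is a maximum. The Table 1 tests in these cohorts precede the second dose and say nothing about the period after it.

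**Is the zero a table-reading artefact?** No. Footnote g is prose and names only Day -1, and SAP Appendix B agrees in both its grid and its footnote.

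**Does other text add a test?**
- Table 6 (Section 9.5) and SAP Table 7 give a serum test at screening and Day 120 only, and otherwise defer to specified visits. Table 6 footnote e says only that the test is done as indicated. Table 2 specifies no post-dose test, and under its footnote a the last visit is Day 168, not Day 120.
- The pregnancy stopping rule in Section 7.4.1 covers only the time before the second dose.
- Section 7.4.2 encourages withdrawing subjects to complete OV4. In Table 2 that visit contains no test.

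**Length of the untested interval.** There is no Day 0, so Day -1 to Day 1 is 1 day and Day 1 to Day 168 is 167 days. The last scheduled test is therefore 1 + 167 = 168 days before the last clinic visit. Day 206 is 206 − 1 = 205 days after dosing, which is the end of the contraception period, and no sample can be taken by telephone.

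**Subjects concerned.** The four cohorts have 8 CD388 and 3 placebo subjects each: 4 × 8 = 32 and 4 × 3 = 12, total 44. Women of childbearing potential who receive the second dose are an unstated subset.

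**Missed opportunities.** Five on-site time points after the second dose (Days 30, 45, 84, 126 and 168) already carry blood counts, serum chemistry and urinalysis.

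**The case against.** The strongest objection is that Table 2 is unaligned rather than deliberately silent. Its footnote j still cites outpatient visits on Days 60, 90 and 120, footnote k cites Day 90, and Section 6.5 promises visits similar to those after the first dose. Read together with Table 6, one might infer a serum test at the last visit. This does not hold: footnote j concerns PK samples and conflicts with footnote a, and Table 6 leaves visits to the schedule. It does suggest that the gap is an oversight.

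Second, detection is not strictly limited to self-report. Targeted physicals, adverse-event review and concomitant-medication review occur on Day 30 and at every outpatient visit, and Sections 9 and 11.2 allow unscheduled tests. That stands. What is missing is a scheduled test, so detection depends on someone already having a reason to look.

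Third, the comparator counts carry some doubt. The missing Day 30 mark in protocol Table 1 and the five rather than six marks in SAP Appendix C may be extraction losses. Table 3 footnote o also describes the Day 206 adverse-event assessment as a telephone call, although the grid marks clinic procedures there. Whether the comparators are 4 or 5 and 5 or 6, Table 2 remains at 0.

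Fourth, the exposure is modest. The 168 days include the inpatient stay to Day 30, when conception is unlikely. The 44 include men, women who cannot conceive and placebo subjects. No further dose follows, and highly effective contraception is required. All of this limits the urgency. Against it, Appendix 1, which criterion 3a cites for examples, accepts abstinence, pills, and condom with spermicide, so contraceptive failure remains plausible.

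**Conclusion.** The concern holds. Table 2 schedules no pregnancy test after the second dose, against 4 or 5 after the first dose and 6 (5 in the SAP extraction) after 900 mg. Women who leave early after the second dose also have no exit test. The gap spans 168 days to the last clinic visit, within a 205-day contraception period.

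This is a safety-monitoring inconsistency that should be corrected. It does not threaten the trial's conclusions: the Day -1 test protects the dosing decision, and no endpoint, analysis or statistical figure depends on it. The practical weight rests on two things the documents do not give: how many women of childbearing potential are in these cohorts, and how many second doses were still to be given.

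**What to change.** In Table 2 and its footnote g, and in SAP Appendix B, schedule for women of childbearing potential a urine pregnancy test on Day 30 and at OV1, OV2 and OV3, and a serum test at OV4 (Day 168). Footnote b then gives early discontinuers an exit test without further change.

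Two wording corrections belong with it. In Table 6 and SAP Table 7, replace Day 120 with the last scheduled clinic test visit of each schedule. In the Table 3 pregnancy footnote, replace OV4 with the intended day (168 or 206).

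The cost is 4 urine + 1 serum = 5 inexpensive tests per woman, with no extra visit or sample collection, plus a protocol amendment with IRB approval and the matching SAP edit. The change leaves Day 168 to Day 206 (206 − 168 = 38 days) without a test, because the final contact is by telephone. Closing that interval would need an added visit, which is not proposed here.
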